## 9. STATISTICAL METHODS INTERIM ANALYSIS PLAN

- Statistical Analysis Plan (SAP), Version 1.0, 15 April 2021
- Statistical Analysis Plan, Interim for Final Analysis, Changes to Planned Statistical Analyses Form, 16 March 2022

## COVID-19 Statistical Analysis Plan

ATEA Pharmaceuticals  
Protocol AT-03A-001  
Page 3 of 77

## MODIFICATION HISTORY

Unique Identifier for this Version	Date of the Document Version	Author	Significant Changes from Previous Authorized Version
V1.0	15Apr2021	[REDACTED]	Not Applicable – First Version

Document: \\[REDACTED]\net\enterprise\Apps\sasdata\SASb\SAS\Atea\_Pharmaceuticals\AT-527\ZSA63631\Biostatistics\Documentation\SAP\AT-03A-001\_V1.0\_COVID\_SAP\_PA7.doc  
Author: [REDACTED] Version Number: V1.0  
Version Date: 15Apr2021  
Template No.: CS\_TP\_BS016 Revision 6 Reference: CS\_WI\_BS005  
Effective Date: 02Dec2019  
Copyright © 2009, 2010, 2012, 2016, 2018, 2019 [REDACTED] All rights reserved. The contents of this document are confidential and proprietary to [REDACTED] Holdings Inc. and its subsidiaries. Unauthorized use, disclosure or reproduction is strictly prohibited.

## COVID-19 Statistical Analysis Plan

## ATEA Pharmaceuticals Protocol AT-03A-001

Page 4 of 77

## 2.3. EXPLORATORY OBJECTIVES

The exploratory objectives are:

- Plasma concentrations of AT-527 and metabolites will be monitored in sparse samples collected from subjects with COVID-19.

## 3. STUDY DESIGN

### 3.1. GENERAL DESCRIPTION

This is a phase 2 double-blind, placebo-controlled, randomized treatment study evaluating AT-527 (or placebo) for 5 days in combination with supportive standard of care (SoC) compared to SoC alone in hospitalized/confined subjects with moderate COVID-19 disease and risk factors for poor outcomes. The study will enroll adults, age  $\geq 18$  years of age, with moderate COVID-19, not on a ventilator. Subjects must also have at least one of the known common risk factors for poor outcomes: obesity (BMI $>30$ ), hypertension, diabetes or asthma. Subjects will be documented as SARS-CoV-2 positive in an assay granted Emergency Use Authorization (EUA) by the U.S. Food and Drug Administration (FDA).

Moderate disease will be defined by the following:

- Symptoms of lower respiratory infection with COVID-19, with initial symptom onset within 5 days prior to Screening:
  - At least 1 of the following: fever ( $> 38.3^{\circ}\text{C}$ ), cough, sore throat, fatigue/malaise, headache, muscle pain, or more significant lower respiratory symptoms including dyspnea (at rest or with exertion)
- Clinical signs indicative of lower respiratory infection with COVID-19 (as above), with:
  - $\text{SpO}_2 \geq 93\%$  on room air or requires  $\leq 2\text{L}/\text{min}$  oxygen by nasal cannula or mask to maintain  $\text{SpO}_2 \geq$

Document: \[REDACTED]\net\enterprise\Apps\sasdata\SASb\SAS\Atea\_Pharmaceuticals\AT-527\527\527A63631\Biostatistics\Documentation\SAP\AT-03A-001\_V1.0\_COVID\_SAP\_PA7.doc

Author: \[REDACTED] Version Number: V1.0  
Version Date: 15Apr2021

Template No.: CS\_TP\_BS016 Revision 6

Reference: CS\_WI\_BS005

Effective Date: 02Dec2019

Copyright © 2009, 2010, 2012, 2016, 2018, 2019 \[REDACTED] All rights reserved. The contents of this document are confidential and proprietary to \[REDACTED] Holdings Inc. and its subsidiaries. Unauthorized use, disclosure or reproduction is strictly prohibited.

COVID-19 Statistical Analysis Plan

ATEA Pharmaceuticals  
Protocol AT-03A-001  
Page 12 of 77

93%

Subjects will be randomized 1:1 (active:placebo). Subjects will receive one (1) tablet of 550 mg active drug (or matching placebo) every ~12 hours to complete **5 days** of treatment.

**Table A Study Design**

Disease Severity	Treatment Duration	Dosing Arms	
Moderate	5 days	active	550 mg AT-527 administered every ~12 hours (10 doses) + SOC
		placebo	AT-527 placebo administered every ~12 hours (10 doses) + SOC

\*Randomized 1:1 (active:placebo)

A cohort of 20 subjects will initially be enrolled to preliminarily assess the safety of the 550 mg BID dosing regimen. Enrollment will be paused after the first 20 subjects, until the Data Safety Monitoring Board (DSMB) conducts a safety review. If study stopping criteria are not met, a second cohort of 20 subjects will be enrolled. Again, enrollment will be paused until the DSMB conducts a safety review of these data.

Subsequent pauses in enrollment will accommodate further DSMB reviews of safety data at enrollment milestones of 50% and 75% of the full enrollment target.

For each interim safety review, pooled safety data will be reviewed by the DSMB. The DSMB will alert the Sponsor if there are any safety concerns for active-treated subjects compared to placebo recipients.

### **3.2. SCHEDULE OF EVENTS**

Schedule of events can be found in Section 6 of the protocol (Table 6-1).

### **3.3. CHANGES TO ANALYSES FROM PROTOCOL**

- “Sparse plasma PK analyses, to assess PK parameters of AT-527 in COVID-19 subjects compared to PK data obtained in healthy human volunteers and HCV subjects” are specified in the protocol Section 8.2.4 but are

Document: \[REDACTED]\net\enterprise\Apps\sasdata\SASb\SAS\Atea\_Pharmaceuticals\AT-527\SAZ\A63631\Biostatistics\Documentation\SAP\AT-03A-001\_V1.0\_COVID\_SAP\_PA7.doc  
Author: \[REDACTED] Version Number: V1.0  
Template No.: CS\_TP\_BS016 Revision 6 Version Date: 15Apr2021  
Effective Date: 02Dec2019 Reference: CS\_WI\_BS005

Copyright © 2009, 2010, 2012, 2016, 2018, 2019 \[REDACTED] All rights reserved. The contents of this document are confidential and proprietary to \[REDACTED] Holdings Inc. and its subsidiaries. Unauthorized use, disclosure or reproduction is strictly prohibited.

ATEA Pharmaceuticals  
Protocol AT-03A-001

## COVID-19 Statistical Analysis Plan

Page 13 of 77

not included in this SAP. This is because only subjects diagnosed with COVID-19 are enrolled in this study. Plasma concentrations of study drug will be listed and summarized as applicable. 21DEC2020

- Per Protocol (PP) set will not be used for this study as for COVID-19 studies it is strongly recommended not to perform analyses based on a PP analysis set due to the short duration of the study, expected high number of protocol deviations and based on current regulatory guidelines and advice. 12Feb2021
- Modified Intent-to-Treat (mITT) analysis set is added in order to run the efficacy analysis excluding the subjects with negative SARS-CoV-2 test at baseline and who did not receive treatment. 12Feb2021
- Analysis of CRP (if quantified) is added. 12Feb2021
- Exploratory analysis of COVID-19 symptoms resolution, COVID-19 symptom severity and time to first SARS-CoV-2 negative test is added. 12Feb2021
- Analysis of change from baseline in antibody to SARS-CoV-2 (IgG and IgM). 09Mar2021
- Addition of an exploratory endpoint to run a similar analysis as Primary analysis but with a different threshold (PRI defined as a  $\geq 1$ -tier increase from baseline). 09Mar2021
- Analysis of the secondary endpoint proportion of subjects Improving/Worsening from baseline in Clinical status has been updated to include more granularity. 09Mar2021
- Addition of an exploratory Time-weighted average change from baseline in quantitative SARS-CoV-2. 09Mar2021
- Definition of “Duration of hospitalization/confinement for COVID-19” was updated, Status 6 on the NIAID Clinical Status scale will not be considered as hospitalization and subjects with hospital discharge will be included. 09Mar2021
- TEAE definition updated to update the time frame to 28 days after last dose of study drug. 09Mar2021
- Addition of an exploratory endpoint: Level of SARS-CoV-2 infectious virus titer. 12Mar2021

Document: \\[REDACTED]\net\enterprise\Apps\sasdata\SASb\SAS\Atea\_Pharmaceuticals\AT-527\SAZ\A63631\Biostatistics\Documentation\SAP\AT-03A-001\_V1.0\_COVID\_SAP\_PA7.doc  
Author: [REDACTED] Version Number: V1.0  
Template No.: CS\_TP\_BS016 Revision 6 Version Date: 15Apr2021  
Effective Date: 02Dec2019 Reference: CS\_WI\_BS005

## 4. PLANNED ANALYSES

### 4.1. DATA SAFETY MONITORING BOARD

A DSMB SAP, describing the methodology and the presentation of and access to results will be provided by [REDACTED] as a separate document.

### 4.2. INTERIM ANALYSIS

An administrative interim analysis will be carried out when the first 70 patients randomized have had follow-up to at least Day 14. The purpose of this analysis is to inform the planning of future clinical studies. The results will not be used to declare evidence of efficacy for the study, but a small alpha spend (0.0001) will be taken for this look. The analysis will be carried out by an independent statistician and interpreted by a small number of members of the Sponsor study team and appropriate senior management personnel, who will be unblinded at the treatment group level. It is acknowledged by the Sponsor that disclosure of interim results to members of the Sponsor study team will impact the interpretation of results of subsequent analyses, i.e. efficacy results may be considered as exploratory.

### 4.3. FINAL ANALYSIS

All final, planned analyses identified in this SAP will be performed by [REDACTED] Biostatistics following Sponsor authorization of this SAP, Sponsor authorization of the analysis sets, database lock (DBL), and general study unblinding.

## 5. ANALYSIS SETS

### 5.1. ALL SCREENED SUBJECTS ANALYSIS SET

The all screened subjects (SCRN) analysis set will contain all subjects who provide informed consent for this study.

Document: \[REDACTED]\net\enterprise\Apps\sasdata\SASb\SAS\Atea\_Pharmaceuticals\AT-527\SAZ\A63631\Biostatistics\Documentation\SAP\AT-03A-001\_V1.0\_COVID\_SAP\_PA7.doc  
Author: [REDACTED] Version Number: V1.0  
Template No.: CS\_TP\_BS016 Revision 6 Version Date: 15Apr2021  
Effective Date: 02Dec2019 Reference: CS\_WI\_BS005

Copyright © 2009, 2010, 2012, 2016, 2018, 2019 [REDACTED] All rights reserved. The contents of this document are confidential and proprietary to [REDACTED] Holdings Inc. and its subsidiaries. Unauthorized use, disclosure or reproduction is strictly prohibited.

## 5.2. INTENT-TO-TREAT ANALYSIS SET

The Intent-to-Treat (ITT) analysis set will contain all subjects in the SCRN analysis set who were randomized to study drug.

For analyses and displays based on ITT analysis set, subjects will be classified according to randomized treatment.

## 5.3. MODIFIED INTENT-TO-TREAT ANALYSIS SET

The Modified Intent-to-Treat (mITT) analysis set will contain subjects in the ITT analysis set with positive qualitative SARS-CoV-2 RT-PCR test result at baseline from the central laboratory and who receive at least one dose of study drug (AT-527 or placebo).

For analyses and displays based on mITT analysis set, subjects will be classified according to randomized treatment.

## 5.4. SAFETY ANALYSIS SET

The safety (SAF) analysis set will contain all subjects in the SCRN analysis set who receive at least one dose of study drug (AT-527 or placebo). If there is any doubt whether a subject was treated or not, he/she will be assumed treated for the purposes of analysis.

For analyses and displays based on the SAF analysis set, subjects will be classified according to the actual treatment received.

## 5.5. PHARMACOKINETIC ANALYSIS SET

The pharmacokinetic (PK) analysis set will contain all subjects in the SCRN analysis set who were randomized to and received at least one dose of AT-527, and for whom evaluable plasma concentration data are available. Subjects who received placebo will not be included in the PK analysis set. If there is any doubt whether a subject was treated or not, he/she will be assumed treated for the purposes of analysis.

## 5.6. PROCESS FOR ANALYSIS SET ASSIGNMENT

The analysis sets that will be used to summarize, analyze, and list the data collected during the course of this study

Document: \[REDACTED]\net\enterprise\Apps\sasdata\SASb\SAS\Atea\_Pharmaceuticals\AT-527\SAZ\A63631\Biostatistics\Documentation\SAP\AT-03A-001\_V1.0\_COVID\_SAP\_PA7.doc  
Author: \[REDACTED] Version Number: V1.0  
Template No.: CS\_TP\_BS016 Revision 6 Version Date: 15Apr2021  
Effective Date: 02Dec2019 Reference: CS\_WI\_BS005

Copyright © 2009, 2010, 2012, 2016, 2018, 2019 \[REDACTED] All rights reserved. The contents of this document are confidential and proprietary to \[REDACTED] Holdings Inc. and its subsidiaries. Unauthorized use, disclosure or reproduction is strictly prohibited.

are all defined based on objective criteria only. That is, none of the analysis set definitions included in this SAP contains subjective criteria (e.g., major protocol deviation potentially having an impact on the efficacy data). Hence, the authorization of this SAP will also stand as the agreement and authorization of the inclusion/exclusion of each subject in each analysis set.

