## 16.2. SECONDARY EFFICACY

### 16.2.1. KEY SECONDARY EFFICACY ENDPOINTS

#### 16.2.1.1. Change from Baseline in Quantitative SARS-CoV-2

The first key secondary endpoint is the change from baseline in amount of quantitative SARS-CoV-2 as measured by RT-PCR at the time points required in the protocol schedule of assessments (Days 2, 5, and 14). Quantitative SARS-CoV-2 will be assessed quantitatively via the TaqPath assay, and qualitatively via a separate assay, COBAS.

Analysis will be performed on the mITT analysis set only.

#### 16.2.1.2. Time to Clinical Recovery (days) by Day 14

The second key secondary endpoint is time to clinical recovery in days on or before Day 14, defined as

- Time to clinical recovery by Day 14 (days) = (Date of clinical recovery on or before Day 14 – Date of randomization) +1

Clinical recovery is defined as achieving the NIAID clinical status of level 6 or above, which include subjects who are no longer hospitalized (level 7 or 8) or hospitalized but not requiring supplemental oxygen (level 6). The clinical status and assessment date/time will be reported on the Ordinal Scale for Clinical Severity page of the eCRF.

The date of clinical recovery is based on the date the score is first  $\geq 6$ . Should there be no clinical recovery, then the time to clinical recovery is set to 15 days.

The 8 levels of NIAID are the following:

1. Death
2. Hospitalized, on invasive mechanical ventilation or ECMO
3. Hospitalized, on non-invasive ventilation or high flow oxygen devices
4. Hospitalized, requiring supplemental oxygen

Document: \\[REDACTED]\net\enterprise\Apps\sasdata\SASb\SAS\Atea\_Pharmaceuticals\AT-

527\SAZ63631\Biostatistics\Documentation\SAP\AT-03A-001\_V1.0\_COVID\_SAP\_PA7.doc

Author: [REDACTED]

Version Number: V1.0

Version Date: 15Apr2021

Template No.: CS\_TP\_BS016 Revision 6

Reference: CS\_WI\_BS005

Effective Date: 02Dec2019

Copyright © 2009, 2010, 2012, 2016, 2018, 2019 [REDACTED] All rights reserved. The contents of this document are confidential and proprietary to [REDACTED] Holdings Inc. and its subsidiaries. Unauthorized use, disclosure or reproduction is strictly prohibited.

5. Hospitalized, not requiring supplemental oxygen – requiring ongoing medical care (COVID-19 related or otherwise)
6. Hospitalized, not requiring supplemental oxygen – no longer requires close medical care for COVID-19  

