- Using 65 for age group instead of 70. (Table 14.1.4.1, 14.2.1.3, 14.2.2.3, 14.2.3.3, 14.2.4.3)
- Hypertension co morbidities will use MHTERM=Hypertension instead of baseline diastolic and systolic values. (Tables 14.1.4.1 and 14.1.4.2)
- Updated derivation for symptom resolution: Time to symptom resolution (days) = (Latest post-baseline assessment symptom end date – Date of randomization) +1. (Tables 14.2.4.X)
- We clarified in footnote that we are using both TaqPath and COBAS tests results for mITT population. (See footnotes in tables)
- For titer data we updated AVAL to 1.2 and 0.45 respectively for results <1.5 and <0.75 in summaries:
  - o It is as per Atea's virologist request and the logic is (Tables 14.2.5.5 and 14.2.4.6):
    - For "<1.5", we should use 15.8, i.e.  $[10^{1.5}]/2$ , as the untransformed value which is 1.2 on log10 scale.
    - For "<0.75", we'll use 2.8, i.e  $[10^{0.75}]/2$ , as the untransformed value which is 0.45 on the log10 scale.
- Time to Sustained Non-detectable SARS-CoV-2 will be displayed by method (COBAS/ TaqPath). (Table 14.2.5.4)
- Level of SARS-CoV-2 Infectious Titer analysis will use the same approach as for the "Time to sustained non-detectable SARS-CoV-2 (mITT)" output, we will be providing estimates of proportion of subjects with undetectable/negative results, using K-M estimates. (Table 14.2.5.6)
- For all tests except ANCOVA, the 2-sided pvalue will be displayed.
- Childbearing potential and HgbA1c are not included in Demographics and baseline characteristics table. (Tables 14.1.4.1 and 14.1.4.2)
- ANCOVA analysis: Present the Change-from-Baseline LSM (SE) for each treatment group. (Table 14.2.5.1)
- Subject level deviations and site level deviations are listed separately.
- Information present in the SAP which are not presented:
  - o Subjects with screen failure.
  - o Inclusion and exclusion summary.
  - o Deviation summary.
  - o Medical History summary.
  - o Disease history summary.
  - o Medication summary.
  - o Exposure summary.

Form No: CS\_FM\_BS006 Revision 8  
Effective Date: 15Jan2020

Reference: CS\_WI\_BS005, CS\_WI\_BS013

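### The post-unblinding changes form moves the planned age cut from 70 to 65 and records two assays for mITT without a rule for discordant subjects; the planned versions should be shown alongside

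*SAP*

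**What the plan says.** **mITT.** SAP 5.3 (and protocol 8.1.3 in the same terms) admits randomized subjects with a "positive qualitative SARS-CoV-2 RT-PCR test result at baseline from the central laboratory and who receive at least one dose of study drug". No assay is named. SAP 16.2.1.1 assigns the roles: viral RNA is "assessed quantitatively via the TaqPath assay, and qualitatively via a separate assay, COBAS". SAP 16.2.3.4 adds that both assays return a detectable or non-detectable result, each with its own detection limit, and asks for separate analyses by assay.

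**Sign-off.** SAP 5.6 treats every set as objectively defined, so that "the authorization of this SAP will also stand as the agreement and authorization of the inclusion/exclusion of each subject in each analysis set". SAP 4.3 nevertheless lists "Sponsor authorization of the analysis sets, database lock (DBL), and general study unblinding" among the steps before the final analysis.

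**Age.** SAP 7.7 sets the age subgroup at below 70 versus 70 and over. SAP section 10 uses the same split for the baseline table.

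**The form.** The Changes to Planned Statistical Analyses Form, dated 16 March 2022, says of age: "Using 65 for age group instead of 70". It applies this to Tables 14.1.4.1, 14.2.1.3, 14.2.2.3, 14.2.3.3 and 14.2.4.3. On mITT it reports a footnote clarification that "we are using both TaqPath and COBAS tests results for mITT population". It traces its changes to work on table shells and interim outputs, says the interim outputs will serve as the final delivery, and says the SAP will not be updated.

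**The concern.** Fixing a population and a subgroup cut in advance ensures that neither can be picked because of the result it gives. Here the age cut departs from the written plan, and the document recording the departure postdates unblinding. The mITT entry bears on a definition that the SAP leaves open exactly where two assays disagree.

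mITT is the only set for the viral-load comparison (SAP 16.2.1.1) and for sustained clearance (SAP 16.2.3.4). After the form's deletions, the mITT repeat is also the only PRI sensitivity analysis left. Subgroups are the only PRI supplementary output left. So the two items affected are among the few supporting results that will be reported. A reader who cannot see the planned version cannot judge whether the change mattered.

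**Working it through.** No stated figure needs reproducing. The check is a comparison of texts, followed by a look at what the counts can and cannot show.

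**1. Timing.** The SAP is version 1.0 of 15 April 2021; the form is dated 16 March 2022, 11 months later. Both timing options printed on the form fall after unblinding, so the conclusion does not depend on which was ticked. Protocol 1.1 (rationale for Amendment 8) already reports an arm-level difference of 0.7 log10 at Day 2. Under SAP 4.2, some sponsor staff saw interim results by treatment group. The form gives no decision date for any entry.

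**2. Age cut.** Plan: 70, in two places. Form: 65, in five tables, one in the baseline series and four in the 14.2 series. No reason is given and no table at 70 is mentioned. SAP 7.7 drops a subgroup split when one side holds less than 5% of subjects. Taking the 81 subjects randomized in Part A, that means 4 or fewer (4/81 = 4.9%; 5/81 = 6.2%). A sparse older group might explain the move, but the form does not say so, and the 5% rule does not cover the baseline table in section 10.

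**3. Who is in mITT.** For dosed subjects, the possible readings give:

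| COBAS | TaqPath | COBAS only | Either positive | Both positive |
|---|---|---|---|---|
| + | + | in | in | in |
| + | − | in | in | out |
| − | + | out | in | out |
| − | − | out | out | out |

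The two middle rows are the discordant subjects. SAP 5.3 does not choose among the columns. SAP 16.2.1.1 points to the first, SAP 16.2.3.4 makes the others possible, and the form mentions both assays without an either/both rule.

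**4. Effect by analysis.** Protocol 8.3.2 limits the Part A viral-load ANCOVA to measurable baseline viral load, and SAP 16.2.4.1 lists summaries for baselines above the TaqPath quantification limit. Anyone quantifiable on TaqPath is TaqPath-detectable, so only rows 1 and 3 remain. There the both-positive rule selects the same subjects as COBAS only, and the either-positive rule can only add row 3. The PRI repeat on mITT has no such restriction, so all rows matter there.

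**5. Counts.** Protocol 1.1 gives 70 interim subjects, 62 evaluable for virology and 58 with quantitative baseline data.

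- Not evaluable: 70 − 62 = 8 (8/70 = 11.4%). The reasons are not given.
- Evaluable without quantitative baseline: 62 − 58 = 4 (4/62 = 6.5%).
- If the 62 were the COBAS-positive dosed set (an assumption), an either-positive rule could add 0 to 8 of the first 70, and a both-positive rule could remove an unknown number. If the 62 already reflects both assays, these figures do not apply.

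**6. Illustration only.** Assume 58/2 = 29 per arm and one reclassified subject lying 2 to 3 log10 from the arm mean. The raw mean moves by about 2/29 = 0.07 to 3/29 = 0.10 log10, or 0.07/0.7 = 10% to 0.10/0.7 = 15% of the interim difference (rounded). The 2 to 3 log10 is not from the documents, and the ANCOVA adjusts for baseline, so this is not an estimate of effect.

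**The case against.** The case on the other side is substantial, and most of it stands as a limit on the point.

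- A reader might infer that the two assays replaced a single prespecified test. The documents do not show that. SAP 5.3 names no assay, both assays give a qualitative result, and the form words its entry as a clarification. The entry might even describe which results are displayed for mITT subjects rather than who they are, although display of clearance by assay has its own separate entry. The table footnotes and shells are not among the documents and may contain the rule.
- A reader might infer that the age change breaches SAP 5.6. It does not: age is a subgroup category, not an analysis set. The departure is from SAP 7.7 and section 10. For mITT, SAP 4.3 lists a separate authorization of the analysis sets that could have settled the assay question; the form cites none.
- A reader might infer that the choices were made with results in view. Only the date of documentation is shown to follow unblinding. The form places the origin in shell and interim-output work, and age and baseline assay status are fixed before dosing. That last fact does not remove the issue, since it is the cut or rule, not the variable, that can be chosen late.
- A reader might infer that mITT could fall to 58. That number counts quantitative baseline data, not double positives. The other 4 may be missing, or detectable but below the quantification limit.
- The stakes are low: SAP 4.2 accepts that efficacy may be considered exploratory, SAP 7.7 disclaims subgroup power, SAP 16.1.5 asks only for counts and proportions in PRI subgroups, Part B is only listed, and the form discloses its own changes.

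What remains is that the planned age split is absent without a reason, and that the documents provided do not determine the membership of discordant subjects.

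**Conclusion.** The point holds as a small, inexpensive improvement. The change of age cut from 70 to 65 is explicit, unexplained, and recorded on a form completed after unblinding. The mITT entry, recorded at the same time, leaves discordant subjects unclassified in the documents provided. The number of subjects whose membership turns on the assay rule cannot be derived and may be zero. For the viral-load ANCOVA, the only possible change from a COBAS-only set is the addition of COBAS-negative, TaqPath-quantifiable subjects.

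This rests on two readings: that the mITT entry concerns membership, and that no unseen footnote or earlier authorization already fixes the rule. If either is wrong, the mITT half reduces to citing that source. The age half is unaffected. Nothing here shows that a definition was chosen because of the results.

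**What to change.** **Age.** Present the five tables at the planned below 70 versus 70 and over, with 65 shown as a labelled post hoc version. Where the 5% rule in SAP 7.7 suppresses a subgroup split, say so with the count; the baseline table can be shown at 70 regardless.

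**mITT.** Run the mITT tables (viral load, TWACFB, sustained clearance, infectious titre, PRI on mITT) on subjects COBAS-positive at baseline and dosed. Show them beside the two-assay set, stating its either/both rule and the date it was decided, and list every subject whose membership differs. COBAS-positive is the reading nearest to SAP 16.2.1.1; it should be described that way, since SAP 5.3 does not name it. If no subject is discordant, one sentence saying so replaces the second set of tables.

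**Cost.** One additional subject flag, the planned age grouping, a repeat run of existing programs, a short listing and a few lines added to the form. The downside is a second set of tables to read.
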